13.1 Primary Efficacy Variable

Improvement of renal function (SCr) from Day 1 through end of treatment, repeated measure analysis. SCr will be collected at baseline and daily from Day 1 through end of treatment.

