13.2 Secondary Efficacy Variables

- Improvement of renal function (SCr) from Day 1 through end of treatment, repeated measure analysis as compared to the Retrospective Control Group.
- For the Prospective Terlipressin Group alone and also in comparison to the Retrospective Control Group:
 - Incidence of dialysis by Day 30 and Day 90 of follow up.
 - Survival by Day 30 and Day 90 follow up.
 - Transplant by Day 30 and Day 90 follow up.
 - Serum creatinine at Day 30 and Day 90 follow up
 - Serum creatinine and incidence of dialysis at Day 30, Day 90, Day 180, and Day 365 after liver transplantation
 - Incidence of kidney transplant within one year after liver transplant
 - Descriptive analysis of number simultaneous liver kidney transplants and episodes of graft rejection at Day 90 and Day 365 after liver transplant

14 Serious Adverse Events

Only Serious Adverse Events will be collected for this study for the prospective group only. Safety review and assessments will be made only for the Prospective Terlipressin Group from time of first dose through 30 days after end of treatment. SAEs are collected from the start of study drug until 30 days after study drug was discontinued. Non-serious Adverse Events are not required to be collected for this study.

The investigator will record the nature, causality, severity, treatment, and outcome of the SAE, and will determine whether there is a “reasonable probability” that the study drug treatment caused the event.

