15.1 Primary Analysis

The primary analysis will utilize mixed effects regression modeling to estimate changes in serum creatinine (SCr) over the study period, accounting for baseline SCr and the correlation structure between the repeated measures. All potential confounders will be added to the model and sequentially removed if they do not confound the association between receipt of terlipressin and improvement in Scr. Those confounders resulting in a $\geq 10\%$ change in the coefficient for the association between terlipressin and improvement in SCr will be retained in the final model. For all generated models, Aikaike Information Criteria (AIC) scores will be calculated and compared. The model with the smallest absolute AIC value will be accepted as the most parsimonious and will be used as the primary model for the explanation of study results. As has been undertaken in other terlipressin studies in HRS, a least-squares means analysis will be conducted using a repeated-measures analysis of variance. The results from this approach to the statistical analysis can then be directly compared to prior study results.

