15.3 Sample Size Considerations

A formal sample size calculation is not applicable for the proposed study. However, at least 50 subjects across more than 5-10 institutions may receive terlipressin treatment during the course of the intervention portion of the study. For the comparison of the terlipressin treatment group and retrospective controls, we expect to have 50 subjects in the intervention group and 150 subjects, assembled from the study sites, in the control group. Assuming a type 1 error of 0.05 and power of 80%, we expect to be able to detect a range of differences in serum creatinine (SCr) depending on the standard deviation of the change (primary endpoint) expected for the groups (see below). Based on results from the REVERSE trial, a change in SCr of as small as 0.05 mg/dL would be able to be detected if the standard deviation for the change approximated 0.10 mg/dL and a pre-specified sample size of 200 subjects, 50 of whom are in the intervention arm, is used for the calculation.

	Δ SCr mg/dL				
Detectable Difference	0.46	0.34	0.23	0.11	0.05
Standard Deviation	1.00	0.75	0.50	0.20	0.10

Given the relatively small number of subjects proposed for inclusion in this terlipressin study, we will likely be underpowered to detect a difference in the other secondary outcomes being explored.

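### The primary SCr contrast is defined in two incompatible ways: change in treated patients with no comparator (Synopsis, 5.1, 13.1) and terlipressin versus controls (15.1)

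*Combined protocol and SAP*

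**What the plan says.** **Endpoint sections.** Section 13.1 gives the primary efficacy variable as "Improvement of renal function (SCr) from Day 1 through end of treatment, repeated measure analysis". The Synopsis and 5.1 say the same, and none of the three names a comparator. The Synopsis, 5.1 and 13.2 then list the same variable first among the secondary endpoints, this time as "repeated measure analysis as compared to the Retrospective Control Group".

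**Primary Analysis (15.1).** A mixed-effects model estimates SCr change over the study period, allowing for baseline SCr and the correlation between repeated values. Candidate confounders enter the model and are "sequentially removed if they do not confound the association between receipt of terlipressin and improvement in Scr". Those that move the terlipressin coefficient by 10% or more stay. A repeated-measures least-squares-means analysis is added.

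**Secondary Analyses (15.2).** The list covers dialysis, mortality, liver and kidney transplantation, and SCr at follow-up and post-transplant time points. The on-treatment SCr comparison with controls is not in it. The section sets a two-sided 0.05 significance threshold.

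**Sample size (15.3).** The section says that a formal calculation does not apply, then gives detectable differences "For the comparison of the terlipressin treatment group and retrospective controls". It states "we expect to have 50 subjects in the intervention group and 150 subjects, assembled from the study sites, in the control group", and makes the differences depend on the "standard deviation of the change (primary endpoint) expected for the groups".

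**The concern.** The endpoint sections and the analysis section point to different contrasts. Because the comparison with controls is listed separately as secondary, the primary endpoint must be the change within the terlipressin group alone. The protocol does not use the term single-arm, but no other reading leaves the two list entries distinct. Yet the model under the Primary Analysis heading is built around the "association between receipt of terlipressin and improvement in Scr", which needs untreated patients in the data.

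What is at stake is which result carries the efficacy conclusion of a study labelled Phase 3. A within-arm fall is hard to attribute to the drug. Patients enter because SCr is raised, which invites regression to the mean. Albumin may be given during treatment. Terlipressin may continue for a limited time after dialysis starts, and 15.1 does not say how SCr values on dialysis are handled. Treatment may also run until SCr is judged to have reached its lowest value, so the end of the measurement window depends on the outcome. The controlled difference addresses some of this and brings its own biases. Unless one contrast is named in advance, the choice can be made after both results are known.

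**Working it through.** **1. Can the stated analysis be run on the stated endpoint?**

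- Endpoint (13.1): SCr change in treated patients.
- Model (15.1): confounders are kept or dropped by the change in the coefficient for receipt of terlipressin.
- If all patients are treated, that covariate is constant. Its coefficient cannot be separated from the intercept, so the 10% rule has nothing to act on.
- The opening sentence of 15.1 and the least-squares-means analysis could be run in one arm. The confounder rule cannot.
- Since 15.2 omits the on-treatment comparison, the first secondary endpoint is analysed only under the heading Primary Analysis.

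**2. Which contrast does the 15.3 table describe?**

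Inputs: 50 and 150 patients, type 1 error 0.05 and 80% power (15.3); two-sided testing (15.2). Dropout and within-patient correlation are not stated and were not used.

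- Multiplier: 1.960 + 0.842 = 2.802.
- Two groups: 2.802 × SD × √(1/50 + 1/150) = 2.802 × 0.1633 × SD = 0.4575 × SD.
- One group of 50: 2.802 × SD / √50 = 2.802 × 0.1414 × SD = 0.396 × SD.

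| SD (mg/dL) | Table in 15.3 | Two groups, 50 vs 150 | One group, n = 50 |
|---|---|---|---|
| 1.00 | 0.46 | 0.46 | 0.40 |
| 0.75 | 0.34 | 0.34 | 0.30 |
| 0.50 | 0.23 | 0.23 | 0.20 |
| 0.20 | 0.11 | 0.09 | 0.08 |
| 0.10 | 0.05 | 0.05 | 0.04 |

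Noncentral t versions give 0.460 × SD (198 df) and 0.404 × SD (49 df). A one-sided two-group version gives 0.41 at SD 1.00, which also fails to match. Four of the five entries match the two-sided two-group formula and none matches the single-arm one, so the table describes the contrast that 13.2 calls secondary. The documents give no precision figure for the within-arm change.

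The entry at SD 0.20 is a separate discrepancy. The formula gives 0.4575 × 0.20 = 0.09, and power at the stated 0.11 is about 92%. An SD of 0.25 would give 0.4575 × 0.25 = 0.114, so a typing error is possible but cannot be confirmed.

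**3. Can the two contrasts lead to different conclusions?**

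The following values are assumptions, not taken from the documents: SD of change 1.0 mg/dL, mean fall 0.5 on terlipressin and 0.2 in controls.

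- Within-arm: 0.5 / (1.0/√50) = 0.5 / 0.1414 = 3.54 standard errors, so power is Φ(3.54 − 1.96) ≈ 94%.
- Between groups: (0.5 − 0.2) / 0.1633 = 1.84 standard errors, so power is Φ(1.84 − 1.96) ≈ 45%.

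With these values a significant within-arm fall would often sit beside a non-significant difference from controls. Both figures use simple tests of means rather than the mixed model in 15.1, so they show direction and rough size only.

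**The case against.** Several counter-arguments have force.

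- **No success rule.** A reader might infer that the trial could declare primary success from a within-arm fall alone. The documents do not support that. They state no null hypothesis or success criterion, the Synopsis calls the analysis descriptive, and nothing ties a significant fall to a claim. This limits the point to an undefined primary contrast. It does not remove it, because 15.1 specifies an adjusted model and 15.2 a significance threshold.
- **15.3 is ambiguous.** A reader might take its mention of a primary endpoint as proof of a second, between-group primary. It may label only the variable, SCr change. The section's last sentence refers to the remaining secondary outcomes as other ones, which suggests that the control comparison is itself secondary, as in 13.2. This stands: the table shows which contrast was calculated, not which was meant to be primary.
- **15.1 may cover two endpoints.** It may serve both the primary and the first secondary endpoint. That is possible, but the section does not say so, and the confounder rule still fits only one of them.
- **Non-specific fall.** A reader might infer that a non-specific fall of 0.40 SD would always come out significant. It would do so about 80% of the time, and the documents give no evidence for a fall of that size. Entry criteria limit it in part: patients must show little SCr improvement, or a plateau, after albumin, and those with recent or imminent dialysis are excluded.
- **The historical comparison is weak.** Controls reach back to January 2015 and must have had at least 48 hours of treatment. That bears on which contrast to choose, not on the need to choose one.

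**Conclusion.** The point holds as an inconsistency in the current text. The primary endpoint has no comparator, its comparison with controls is secondary, and the confounder-selected model under Primary Analysis works only for the latter. No section reconciles them. The conflict between 13.1/13.2 and 15.1 is firm and needs no assumption beyond reading the two endpoint entries as distinct. The evidence from 15.3 is supporting only: its figures fit a 50 versus 150 comparison (0.4575 SD, against about 0.40 SD for one arm), but its wording is ambiguous.

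The 94% and 45% power figures depend on the assumed means and SD. They show that the two contrasts can disagree, not that they will. The point should be settled before analysis, because otherwise the result that carries the conclusion can be selected once both are seen.

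**What to change.** Name one primary contrast and make the Synopsis, 5.1, 13.1, 13.2, 15.1, 15.2 and 15.3 agree. The choice is the sponsor's.

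**Option A, closest to 15.1 and 15.3.** Make the adjusted terlipressin-versus-control difference in on-treatment SCr primary, remove it from the secondary lists in the Synopsis, 5.1 and 13.2, and report the within-arm change descriptively. The cost is that the primary result then rests on a non-randomised historical comparison, and the stated primary endpoint changes, so an amendment is needed.

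**Option B.** Keep the within-arm change as primary. Give it its own model without a treatment coefficient and its own precision statement (about 0.40 SD detectable with 50 patients at 80% power, two-sided 0.05). Relabel the 15.1 confounder model and the 15.3 table as belonging to the secondary control comparison, and add that comparison to 15.2. Do not present the within-arm change as evidence of a drug effect.

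Under either option, clarify what 15.3 means by primary endpoint, and separately correct or explain its entry at SD 0.20 (0.11 stated, 0.09 by the formula that reproduces the other entries). Both options change text only and need no new data or patients.

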13.2 Secondary Efficacy Variables

- Improvement of renal function (SCr) from Day 1 through end of treatment, repeated measure analysis as compared to the Retrospective Control Group.
- For the Prospective Terlipressin Group alone and also in comparison to the Retrospective Control Group:
 - Incidence of dialysis by Day 30 and Day 90 of follow up.
 - Survival by Day 30 and Day 90 follow up.
 - Transplant by Day 30 and Day 90 follow up.
 - Serum creatinine at Day 30 and Day 90 follow up
 - Serum creatinine and incidence of dialysis at Day 30, Day 90, Day 180, and Day 365 after liver transplantation
 - Incidence of kidney transplant within one year after liver transplant
 - Descriptive analysis of number simultaneous liver kidney transplants and episodes of graft rejection at Day 90 and Day 365 after liver transplant

14 Serious Adverse Events

Only Serious Adverse Events will be collected for this study for the prospective group only. Safety review and assessments will be made only for the Prospective Terlipressin Group from time of first dose through 30 days after end of treatment. SAEs are collected from the start of study drug until 30 days after study drug was discontinued. Non-serious Adverse Events are not required to be collected for this study.

The investigator will record the nature, causality, severity, treatment, and outcome of the SAE, and will determine whether there is a “reasonable probability” that the study drug treatment caused the event.

14.1 SAE Definitions

The following definitions are based on:

- International Conference on Harmonization (ICH) E2A: International Conference on Harmonisation Tripartite Guideline: Clinical Safety Data Management: Definitions and Standards for Expedited Reporting (1994).
- ICH E6: International Conference on Harmonisation Tripartite Guideline: Guideline for Good Clinical Practice (1996) and Integrated Addendum [E6] (R2) June 2015.

- Office of Human Subjects Protection, Division of Department of Health and Human Services Policy; "Reviewing and Reporting Unanticipated Problems Involving Risks to Subjects or Others and Adverse Events" (2007).
- Code of Federal Regulations Title 21, Part 312.32 (2011).

Also included are events that are common to this subject population.

14.2 Suspected Unexpected Serious Adverse Reaction (SUSAR)

This is an unexpected SAE or suspected unexpected adverse reaction (SUSAR) which is not listed in the Investigator's Brochure (IB), nor listed at the specificity or severity observed. If an SUSAR is listed in the IB as occurring with a specific class of drugs, or occurring as part of a disease process, or from the pharmacological properties of the drug, but not specifically mentioned as occurring with the particular drug under investigation, it should be considered unexpected.

14.3 Serious Adverse Event Definition

Serious adverse events (SAE) are defined (in the view of the investigator or the sponsor) as any untoward medical occurrence that meets any of the following criteria:

- Resulted in death.
- Is life-threatening (if an AE or SUSAR places a subject at risk of death at the time of the event; it does not refer to an event which hypothetically might have caused death if it were more severe).
- Requires inpatient hospitalization or prolongation of existing hospitalization.
- Results in disability (persistent or significant incapacity or substantial disruption of the ability to conduct normal life functions).
- Is a congenital anomaly/birth defect.
- Is an important medical event that may not result in death, be life-threatening, or require hospitalization may be considered serious when, based upon appropriate medical judgment, they may jeopardize the subject and may require medical or surgical intervention to prevent one of the outcomes listed in this definition. Examples of an important medical event include allergic bronchospasm, blood dyscrasias, convulsions that do not result in inpatient hospitalization, or drug dependence/abuse.

14.4 Severity of an Adverse Event

Intensity of an AE, assessed by the investigator and graded as mild, moderate, or severe, irrespective of the relationship to the drug or seriousness of the event, and evaluated according to the following scales:

- Mild - awareness of the symptom but easily tolerated.
- Moderate - discomfort enough to interfere with normal activities.
- Severe - Incapacitating with the inability to perform normal activities.

14.5 Study Drug Causality

Study drug causality will be assessed as follows:

Unrelated: An AE that is clearly and incontrovertibly due to extraneous causes (disease, environment, etc.) and does not meet the criteria for 'possible' or 'probable.'

Possible: The connection between the AE and study treatment appears unlikely but cannot be ruled out with certainty. An AE may be considered 'possibly related' if it has at least 2 of the following:

- It follows a reasonable temporal sequence from administration of study drug.
- It may readily have been produced by the subject's clinical state or by environmental or toxic factors.
- It follows a known response pattern to study drug.

Probable: An AE that is considered to be related to study drug treatment with a high degree of certainty. An AE may be considered probably related if:

- It follows a reasonable temporal sequence from administration of study drug.
- It cannot be reasonably explained by the known characteristics of the subject's clinical state.
- It follows a known pattern of response to study drug treatment.
- It reappears upon rechallenge.

Collaborative Research Study, Version 4: 06/29/21
To Treat HRS-AKI Patients with Continuous Terlipressin Infusion

Table 4 lists adverse events that are common in this subject population (i.e., with HRS), even in the absence of exposure to the study drug (Rozov-Ung and Panesar, 2010; Arroyo et al, 2008). The investigator may use this as a guidance while assessing the causality.

Table 4: Adverse Events Common to the Hepatorenal Syndrome (HRS) Population

MedDRA System Organ Class	Preferred Term
Blood and Lymphatic System Disorders	Anemia Coagulopathy
Cardiac Disorders	Atrial fibrillation Bradycardia
Gastrointestinal Disorders	Abdominal pain Diarrhea Nausea Vomiting
General Disorders and Administration Site Conditions	Multi-organ failure
Hepatobiliary Disorders	Hepatic failure
Infections and Infestations	Pneumonia Urinary tract infection
Metabolism and Nutrition Disorders	Hyperglycemia
Nervous System Disorders	Headache
Respiratory, Thoracic and Mediastinal Disorders	Dyspnea Epistaxis Pulmonary edema Respiratory failure
Vascular Disorders	Hypotension

Source: Rozov-Ung and Panesar, 2010; Arroyo et al, 2008.

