8.4 Administration

Subjects in the Prospective Terlipressin Group:

Single-use, sterile 6-mL vials containing 1 mg of lyophilized terlipressin acetate (equivalent to 0.85 mg terlipressin free base) with 10 mg mannitol as a bulking agent/stabilizer.

- For initial bolus dose of 0.5mg, the vial will be reconstituted with 5 mL of sterile 0.9% sodium chloride solution and given over 1-minute push.
- Continued dosing will be by 2mg infusion per day for Days 1, and 2. For continuous infusion, the dose of terlipressin is to be dissolved in 0.9% sodium chloride solution and infused with a pump.
- If on Day 3 the SCr is not 30% lower from the baseline value, increase infusion dose to 4 mg per day.
- If on Day 5 the SCr is not 50% lower from the baseline value, increase infusion dose to 6-8 mg per day, per PI discretion. Dosing can be increased by more than 1 mg increment at Day 5 or beyond, up to a maximum of 8 mg/day.
- If the subject has infusion stopped for \geq 4 hours, a 0.5 mg bolus should be given prior to restarting infusion.
- The drug should not be used in subjects with severe coronary artery disease or in the setting of circulatory overload, pulmonary edema, or bronchospasm as determined by the Investigator. If drug therapy has been initiated, Investigator can also decide not to increase the dose, based on the patient's status with regard to the above, based on individual subject condition.

- If dosing is interrupted due to an adverse event, terlipressin may be re-started, at the discretion of the investigator, at the same or lower dose as per protocol. Terlipressin will not be restarted if dosing was interrupted due to cardiac ischemia or mesenteric ischemia.

Subjects in the Retrospective Control Group:

The dose and method of administration for Midodrine/Octreotide (M&O), albumin, or other vasopressor will be recorded as noted in the patient's medical record. To be included as a completed subject in this study, patients must have been treated for at least 48 hours with albumin infusions beyond volume resuscitation and diuretic withdrawal. Vasopressors also need to be used for a minimum of 48 hours.

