11.4 Adverse Events

Only Serious Adverse Events will be recorded until 30 days after discontinuation of study drug.

Those events that are unanticipated serious adverse events possibly related to the study drug (SUSAR) must be reported to the sponsor or its designee for safety reporting in an expedited. See section 14.2 for SUSAR definition.

12 Detail of Laboratory Assessments and Procedures

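### The causality scale in section 14.5 is internally inconsistent: Possible credits an alternative cause towards relatedness, Probable has no stated threshold, and some novel SAEs may have no grade

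*Combined protocol and SAP*

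**What the plan says.** Section 14.5 has three grades.

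- **Unrelated** requires a clear and undeniable extraneous cause, and that the event meets neither of the other grades.
- **Possible** is described as a link that looks unlikely but cannot be excluded. An event may be placed there "if it has at least 2 of the following": plausible timing relative to dosing; a ready explanation in the patient's condition or in environmental or toxic factors; agreement with a known response to the drug.
- **Probable** is described as a high degree of certainty. Four criteria follow: plausible timing; no reasonable explanation in the patient's clinical state; a known response pattern; and "It reappears upon rechallenge". The text does not say whether all, any or some number of them must be met.

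The grades are used elsewhere. Section 11.4 says that "unanticipated serious adverse events possibly related to the study drug (SUSAR) must be reported" to the sponsor as an expedited matter. Section 15.4 summarises SAEs by the investigator's view of relatedness as well as by site-reported term. The opening of section 14 asks for a further judgement, whether there is a reasonable probability that the drug caused the event, and does not map it to the three grades. Section 8.4 allows discretionary restart after other adverse events but adds: "Terlipressin will not be restarted if dosing was interrupted due to cardiac ischemia or mesenteric ischemia".

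**The concern.** A causality scale should do three things: give every event a grade, keep the grades in order, and let the absence of another explanation raise the suspicion of a drug cause. On its literal wording this scale does not reliably do any of them. The clinical-state item in Possible works in reverse, and the missing count in Probable leaves each investigator to choose a threshold.

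Only SAEs are collected, and only in the terlipressin group, so there is no control rate against which misattribution would show. If two sites read 14.5 differently, the same SAE could be left ungraded at one and called Probable at the other. The SUSAR flag and the related-SAE summary would then partly reflect how the scale was read.

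**Working it through.** The plan gives no figure on this point, so there is none to reproduce. The check is of the decision rule itself.

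**Inputs (14.5).** Code each item 1 if true and 0 if not: T = plausible timing; C = explained by clinical state or other factors; K = known drug response pattern; R = recurs on rechallenge. Assumption: the second Probable criterion is the opposite of C.

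- Possible score = T + C + K; the list is met at 2 or more.
- Probable score = T + (1 − C) + K + R; threshold not stated, so 4, 3, 2 and 1 are all tried.

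**Step 1. Three well-timed events against the Possible list.**

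- No disease explanation, no known pattern: 1 + 0 + 0 = 1. Not met.
- Disease explanation, no known pattern: 1 + 1 + 0 = 2. Met.
- No disease explanation, known pattern: 1 + 0 + 1 = 2. Met.

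The first two differ only in that the second has an alternative cause, and it is the second that qualifies.

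**Step 2. Where the first event goes instead.** It is not Unrelated, because no extraneous cause is evident. Without rechallenge its Probable score is 1 + (1 − 0) + 0 + 0 = 2. It fails if four or three criteria are needed, and then has no grade. It passes if two or one suffice, and is then Probable although it misses the Possible list.

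**Step 3. All patterns.** Four yes/no items give 2^4 = 16 patterns. The Possible list is met in 8.

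| Criteria needed for Probable | Patterns meeting Probable | Probable but not on the Possible list | On neither list |
|---|---|---|---|
| All 4 | 1 | 0 | 8 |
| At least 3 | 5 | 2 | 6 |
| At least 2 | 11 | 5 | 3 |
| Any 1 | 15 | 7 | 1 |

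Only the all-four reading keeps every Probable event on the Possible list, and it admits a single pattern (T = 1, C = 0, K = 1, R = 1). Under any-one, Probable is the easier test, 15 patterns against 8.

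**Step 4. Events that cannot be rechallenged.** With R = 0 the highest Probable score is 1 + 1 + 1 + 0 = 3. Under the all-four reading, a fatal event, or cardiac or mesenteric ischemia where 8.4 bars restart, can never be Probable. Its highest grade is Possible, which the text describes as an unlikely link.

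**Step 5. Probable redefined as its first three criteria.** T = 1, C = 0, K = 1 with R either 0 or 1 gives 2 of the 16 patterns. Both have T = 1, so both also fall within a Possible grade defined by timing and a drug cause that cannot be excluded. The order of the grades is restored.

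**The case against.** The strongest reply is that 14.5 is guidance and not an algorithm. "An AE may be considered 'possibly related' if it has at least 2 of the following" is permissive, and the lead description (cannot be excluded) could admit a novel event whatever its score. This has some force. But the same description calls the link unlikely, which does not fit a well-timed event with no other explanation, and an investigator who follows the list will exclude it.

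The safeguards also stand. Section 14.12 sends every SAE to the sponsor within 24 hours and to the IRB, whatever its relatedness or expectedness. Section 15.4 summarises SAEs by term too. A separate safety review plan, which is not among the documents, may provide for a sponsor causality review.

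A reader might go further than the text allows in four ways:

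- **That drug-related SAEs are under-called.** Not established. Nothing defaults to Unrelated, which is hard to assign, and looser readings of Probable over-call the same event.
- **That a SUSAR rarely reaches Possible.** With K = 0, only one of the four T and C combinations qualifies, but that counts logical patterns and is not a rate. Nor does an unexpected event always have K = 0: section 14.2 includes events "nor listed at the specificity or severity observed", which may still fit a known pattern.
- **That Probable is unreachable.** This holds only under the all-four reading and only without rechallenge. Restart after other adverse events is allowed.
- **That Table 4 steers events away from the drug.** The table is optional ("The investigator may use this as a guidance while assessing the causality"). On the literal scoring, a listed event gains the clinical-state point and so moves towards Possible. Section 8.4 does say the drug should not be used "in the setting of circulatory overload, pulmonary edema, or bronchospasm as determined by the Investigator", but the protocol does not name bradycardia or respiratory failure as drug concerns.

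**Conclusion.** The concern holds as an inconsistency in a stated rule. A well-timed SAE with neither a disease explanation nor a known pattern misses Possible at 1 of 3, and adding a disease explanation lets it in at 2 of 3. It has no grade if Probable needs three or four criteria, and is Probable if two or one suffice. Depending on the reading, Probable covers between 1 and 15 of 16 patterns, against 8 for Possible. The SUSAR trigger in 11.4 and the relatedness summary in 15.4 are therefore unreliable, with no fixed direction of error.

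This rests on taking the lists literally, on treating the second Probable criterion as the opposite of the clinical-state item, and on R = 0 where the drug is not restarted. The documents do not allow an estimate of how many SAEs would be affected. SAE collection, reporting of SAEs to the sponsor and the efficacy analyses are not affected. The restart rule in 8.4 is not in question.

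**What to change.** Amend 14.5 as follows:

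1. Delete the clinical-state item from Possible and define the grade as a reasonable temporal sequence in which a drug cause cannot be ruled out.
2. Define Probable as meeting its first three criteria, with recurrence on rechallenge as supportive evidence only.
3. State that every SAE not meeting Unrelated counts as at least possibly related, both for SUSAR screening under 11.4 and in the 15.4 summary. Say how the reasonable-probability judgement in section 14 maps to the grades.

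The cost is a wording amendment and a note on completing the CRF. The downside is that more SAEs will be shown as possibly related. No dosing or restart rule changes, and Table 4 can stay as it is.
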